9.10 Other Assessments

Not applicable.

9.11 Health Economics OR Medical Resource Utilization and Health Economics

Health economics/medical resource utilization and health economics parameters will not be evaluated in this study.

10 STATISTICAL CONSIDERATIONS

10.1 Statistical Hypotheses

No hypothesis testing is planned for this study.

10.2 Sample Size Determination

The sample size is based on practical considerations and is consistent with this type of pilot study. Approximately [REDACTED] participants will be enrolled in the study. The minimum size for each subgroup (Cohort 1: MYK-224 monotherapy or SOC with beta-blockers; Cohort 2: SOC with

nondihydropyridine calcium channel-blockers or SOC with disopyramide in combination with beta-blockers or calcium channel-blockers) is [REDACTED].

[REDACTED] per cohort receiving MYK-224 will achieve a 91% power to detect a 30 mm Hg within-group change from baseline in post-exercise peak LVOT gradient and a > 99% power to detect a 50-mm Hg change. This assumed a 1-sided $\alpha = 0.05$ and a common standard deviation (SD) of [REDACTED]. The common SD of [REDACTED] is based on a previous study on a similar compound (MYK-461). Additionally, with smaller SD in both resting and Valsalva peak LVOT gradient, higher powers will be expected in detecting the same magnitude of changes.

The minimum subgroup size of [REDACTED] is determined based on post-exercise peak LVOT gradient. [REDACTED] per subgroup receiving MYK-224 will provide an 81% power to detect a 40 mm Hg within-group change from baseline and a 93% power to detect a 50-mm Hg change (see Table 10.2-1).

Table 10.2-1: Power for Detecting a Statistically Significant Within-Group Change in Post Exercise Peak LVOT Gradient

Subgroup Size	Power (%) to Detect 40-mm Hg Change From Baseline	Power (%) to Detect 50-mm Hg Change From Baseline
[REDACTED]	85	95
[REDACTED]	81	93
[REDACTED]	74	89

The precision of the sample size is addressed based on secondary endpoints as their precision is more challenging to achieve compared with the primary safety endpoints.

10.3 Analysis Sets

For the purposes of analysis, the following populations are defined:

Population	Description
Enrolled	All participants who have agreed to participate in a clinical study following completion of the informed consent process.
Safety	All participants who received at least 1 dose of MYK-224
PK	All enrolled participants who receive at least 1 dose of MYK-224 and have at least 1 evaluable MYK-224 plasma concentration.
Efficacy/PD	All participants who receive at least 1 dose of MYK-224 and have primary or secondary endpoint data, including a baseline value and at least 1 post-baseline value.

10.4 Statistical Analyses

The statistical analysis plan (SAP) will be finalized prior to database lock (DBL), and it will include a more technical and detailed description of the statistical analyses described in this section.

10.4.1 General Considerations

Primary and secondary endpoints will be summarized descriptively. Descriptive summary statistics for continuous variables will include the number of participants, mean, standard deviation, median, minimum, and maximum. Categorical variables will be summarized using counts and percentages. Ninety percent exact confidence intervals will be presented, as appropriate. Baseline will be defined as the last observation recorded before the first dose of MYK-224.

10.4.2 Primary Endpoint(s)

Table 10.4.2-1: Endpoints

Primary Endpoint	Timeframe
Incidence, severity, and causality of AEs and SAEs	Up to 30 days after EOT-A or the final study visit, whichever is longer
Incidence of symptomatic resting LVEF [REDACTED]	Up to EOS-A
Incidence of resting LVEF [REDACTED]	Up to EOS-A
Incidence of MACE, including cardiovascular death, nonfatal stroke, nonfatal myocardial infarction	Up to 30 days after EOT-A or the final study visit, whichever is longer
Incidence of hospitalizations (due to cardiovascular and non-cardiovascular events)	Up to 30 days after EOT-A or the final study visit, whichever is longer
Incidence of HF events (including hospitalizations and urgent emergency room/outpatient visits for HF)	Up to EOS-A
Incidence of atrial fibrillation/flutter (new from screening and recurrent)	Up to EOS-A
Incidence of appropriate implantable cardioverter defibrillator therapy and resuscitated cardiac arrest	Up to EOS-A
Incidence of ventricular tachyarrhythmias (includes ventricular tachycardia, ventricular fibrillation, and Torsades de Pointes)	Up to EOS-A
Results of vital signs, physical exams, 12-lead ECG assessments (including HR), and clinical laboratory tests	Up to EOS-A

Abbreviations: AE, adverse events; ECG, electrocardiogram; EOS, end of study; EOT, end of treatment; HF, heart failure; HR, heart rate; LVEF, left ventricular ejection fraction; MACE, major adverse cardiovascular events; SAE, serious adverse event; [REDACTED].

All safety analyses will be performed on the Safety Population. All recorded AEs and SAEs will be classified and listed by participant. All recorded AEs and SAEs will be summarized by system

organ class, preferred term, and subgroup. The incidence of cardiovascular events, hospitalizations, and arrhythmia will be listed by participants and summarized by subgroup. Clinical laboratory test results, vital sign measurements, 12-lead ECG parameters, TTE parameters, weight, and PE findings will be listed by participants and summarized by planned time point and subgroup. Abnormal laboratory test results will be listed by participants and summarized by subgroup, and normal ranges will be included for reference.

The 12-lead ECG readings will be summarized by planned time point and subgroup and evaluated by the investigator. Abnormalities, if present, will be characterized as either clinically significant or non-clinically significant and listed by participant. HR, PR, QRS, and QTcF will be summarized using descriptive statistics. For each time point of measurement, the changes from baseline will be summarized using descriptive statistics. A categorical analysis of post-dose QTcF values by subgroup will also be performed.

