5 STUDY DESIGN

5.1 Overall Design

This is a Phase 2a, open-label, multicenter, proof-of-mechanism study of MYK-224 in participants with symptomatic oHCM. It will be conducted in up to 2 cohorts with approximately [REDACTED] participants with symptomatic oHCM in each cohort.

Cohort 1 will investigate MYK-224 administered as monotherapy or as an add on to SOC with beta-blockers

Cohort 2 will explore MYK-224 administered as an add on to SOC with nondihydropyridine calcium channel-blockers or SOC with disopyramide (combined with either a beta-blocker or a calcium channel-blocker).

All participants from Cohort 1 and 2 will participate in the main study (Part A). Following the main study period, the [REDACTED] of MYK-224 will be assessed via an optional OLE (Part B).

PART A:

All participants will participate in 3 study periods in Part A:

- Screening Period for Part A (up to [REDACTED])
- Treatment Period (variable between approximately 12 and 45 weeks)
 - Dose Titration period
 - Stable Dosing period
 - End of Treatment for Part A (EOT-A)

- Washout Period

- Washout Visit for Part A (Washout A; [REDACTED])
- End of Study Visit for Part A (EOS-A; [REDACTED])

PART B:

Participants who successfully complete Part A will then be eligible for an optional OLE (Part B). This will last for up to [REDACTED] and include the following:

- Screening B Period ([REDACTED])
- Treatment Period ([REDACTED])
 - Day 1B through End of Treatment for Part B (EOT-B)

[figure not shown]
Washout B Period [REDACTED]

End of Study for Part B (EOS-B) visit following Washout

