5.1.1 Part A - All Participants

The following procedures and study visits apply to all participants enrolled in the study. The study design schematic for Part A is presented in Figure 5.1.1-1.

Figure 5.1.1-1: Study Design Schema (Part A)

Grey boxes represent sections that may be repeated as needed prior to progressing to the next phase of the study.

Abbreviations: EOS-A, end of study for Part A; EOT, end of treatment; PK, pharmacokinetics; QD, once daily; TTE, transthoracic echocardiogram.

^a Dose Titration: Repeat 4-week titration period until target dose is identified or maximum allowable dose is reached.

^b Stable Dosing: Repeat 2-week dosing until participant has been on target dose/maximum allowable dose for at least 6 weeks AND dosed with MYK-224 at any dose for at least 12 weeks.

* TTE from Dose Titration Week 3 will be used to determine titration decision at Week 4.

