6.2 Exclusion Criteria

Participants are excluded from the study if any of the following criteria apply:

PART A:

1) Medical Conditions

- a) Presence of any medical condition that precludes exercise stress testing
- b) History of syncope or sustained ventricular tachyarrhythmia within 6 months prior to Screening
- c) Active infection
- d) Known infiltrative or storage disorder causing cardiac hypertrophy that mimics HCM, such as Fabry disease, amyloidosis, or Noonan syndrome with left ventricular hypertrophy
- e) Has been successfully treated with invasive septal reduction (surgical myectomy or percutaneous alcohol septal ablation [ASA]) within 6 months prior to Screening or plans to have either of these treatments during the study (Note: Individuals with an unsuccessful myectomy or percutaneous ASA procedure performed > 6 months prior to Screening may be enrolled if study eligibility criteria for LVOT gradient criteria are met).
- f) Implantable cardioverter-defibrillator (ICD) placement or pulse generator change within 2 months prior to screening or planned new ICD placement during the study (pulse generator changes, if needed during the study are allowed)
- g) Has a history of resuscitated sudden cardiac arrest (any time) or known history of appropriate implantable cardioverter-defibrillator (ICD) discharge for life-threatening ventricular arrhythmia within 6 months prior to screening
- h) Has paroxysmal atrial fibrillation with atrial fibrillation present per the Investigator's evaluation of the subject's ECG at the time of Screening
- i) Has persistent or permanent atrial fibrillation not on anticoagulation for at least 4 weeks prior to Screening and/or not adequately rate controlled within 6 months prior to Screening (Note: Participants with persistent or permanent atrial fibrillation who are anticoagulated and adequately rate-controlled are allowed. Please see restricted therapies in [Appendix 5](#)).
- j) Has QT interval with Fridericia correction (QTcF) > 500 msec when QRS interval < 120 msec or QTcF > 520 msec when QRS ≥ 120 msec if participant has left bundle branch block or any other 12-lead ECG abnormality considered by the investigator to pose a risk to participant safety (eg, second-degree atrioventricular block type II)
- k) Has known moderate or severe (per investigator's judgment) aortic valve stenosis at screening
- l) History of LV systolic dysfunction (LVEF < 45%) at any time during their clinical course

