9.4.3 Cardiac Monitoring Device (Part A only)

At Screening and in two-week intervals throughout the titration period for Part A, participants will wear a small data collection device that is FDA approved for collecting continuous HR and rhythm data (Table 2-1, Table 2-2, and Table 2-4). The self-contained device attaches to the skin using medical adhesive and contains surface electrodes, internal electronics to capture a continuous single-lead ECG waveform, sufficient solid-state memory to store up to 14 days of data, and a battery to power the device. It has no external wires or other connections and should be kept powered on continuously throughout the recording period. Following the period of data collection, the device will be returned to the study site where the continuous ECG waveforms record stored on the device will be retrieved and uploaded to the central ECG vendor for analysis. The device will be used to explore the pattern of HR and heart rhythm before and during treatment with MYK-224. Additional details regarding the use of this device will be provided in a separate manual.

The device will be applied at the Screening visit and collected at the Day 1A clinic visit. Participants should wear the device for a minimum of 10 days and a maximum of 14 days during screening prior to Day 1A. Each participant should be trained on applying the device and will be provided with additional single-use electrodes to be replaced if needed during the 14-day recording period. The device will be collected on Day 1A prior to dosing. During the titration period, participants will wear the device in two-week intervals. A new device will be applied at each Titration [REDACTED] visit and collected at the following Titration [REDACTED] visit (see Table 2-2).

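### Arrhythmia incidence is a crude percentage of all dosed participants, although patch-monitored time on drug varies about tenfold with the number of titration cycles

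*Combined protocol and SAP*

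**What the plan says.** Table 10.4.2-1 has a primary safety row worded "Incidence of atrial fibrillation/flutter (new from screening and recurrent", followed to EOS-A. Separate rows to the same time point cover ventricular tachyarrhythmias, and appropriate ICD therapy together with resuscitated cardiac arrest. On the analysis set, Section 10.4.2 states: "All safety analyses will be performed on the Safety Population". Section 10.3 defines that set as everyone who received at least one dose. Section 10.4.1 reports categorical variables as counts and percentages, and Section 10.4.2 summarises arrhythmia by subgroup. Neither mentions monitored time or an at-risk subset, and 'new' and 'recurrent' are not defined.

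The monitoring schedule is in Section 9.4.3. For baseline: "Participants should wear the device for a minimum of 10 days and a maximum of 14 days during screening prior to Day 1A". On treatment: "During the titration period, participants will wear the device in two-week intervals". Section 5.1.1 leaves the number of cycles open: "Dose Titration: Repeat 4-week titration period until target dose is identified or maximum allowable dose is reached". Table 2-3 (stable dosing) has no device row. Table 2-4 mentions the device only for its removal if one is being worn. Section 5.1 gives the length of Part A treatment: "Treatment Period (variable between approximately 12 and 45 weeks".

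On eligibility, Section 6.2 (Part A, criterion 1 i) notes: "Participants with persistent or permanent atrial fibrillation who are anticoagulated and adequately rate-controlled are allowed".

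**The concern.** A crude percentage is interpretable when participants are watched for similar lengths of time. Here the length of continuous rhythm monitoring on drug is set by how many titration cycles a person needs. The longer the patch is worn, the more likely it is to catch an episode, whatever the drug does.

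The label 'new from screening' sharpens the problem. A single recording of 10 to 14 days has to establish that a participant was free of AF, and the on-drug period set against it may hold many times more recorded days. There is no control arm and no data monitoring committee, so the screening recording is the main reference for rhythm. An uncorrected percentage could be read as an arrhythmia signal when it reflects only the amount of monitoring.

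The planned summaries are by background-therapy subgroup. Section 5.4 describes verapamil and diltiazem as moderate CYP3A4 inhibitors, and Section 7.4.1.1 allows Cohort 2 a different titration schedule. If cycle counts differ between subgroups for such reasons, the subgroup percentages will differ too.

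**Working it through.** The documents state no expected rate, precision or power for the arrhythmia rows, so there is no planned figure to reproduce.

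**Monitored days.** Inputs:
- Baseline recording b = 10 to 14 days (Section 9.4.3).
- About 14 on-drug days per 4-week cycle (Section 9.4.3, Table 2-2).
- At least 6 weeks at target dose, of which the last cycle supplies 4 (Section 5.1.1.2).
- At least 12 weeks of treatment in total (Section 5.1.1.2), and about 45 at most (Section 5.1).

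With k cycles, treatment lasts max(12, 4k + 2) weeks. Ten cycles take 42 weeks and eleven would take 46, so k is about 1 to 10. On-drug patch time is d = 14k, or 14 to 140 days. Relative to baseline this is 14/14 = 1.0 up to 140/10 = 14.

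The patch covers 14/84 = 17% of treatment days at one cycle and 140/294 = 48% at ten. Dividing by time on treatment would therefore not repair the comparison; the divisor has to be monitored time.

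**No drug effect, events found by the patch alone.** Assume a constant detection rate λ per day, the same before and during treatment.

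- Any event on drug: 1 − exp(−λd).
- AF labelled new: exp(−λb) × (1 − exp(−λd)).

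With b = 14:

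| λ per day | Share labelled new, k = 1 | k = 3 | k = 5 | k = 10 |
|---|---|---|---|---|
| 0.001 | 1.4% | 4.1% | 6.7% | 12.9% |
| 0.005 | 6.3% | 17.7% | 27.5% | 46.9% |

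For example, at λ = 0.005 and k = 10: exp(−0.07) × (1 − exp(−0.70)) = 0.932 × 0.503 = 46.9%. Using b = 10 moves the results by at most about 3 points for λ between 0.0005 and 0.01.

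The ventricular row carries no 'new' label, so the first formula applies. Between 1 and 10 cycles it rises from 1.4% to 13.1% at λ = 0.001, and from 6.8% to 50.3% at λ = 0.005.

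**If people differ in their rates.** Take an assumed 10% chance of detection per 14 days and b = 10. The share labelled new at 1, 5 and 10 cycles is 9.3%, 38.0% and 60.4% with a common rate. It is 8.1%, 27.2% and 39.2% if rates vary strongly between people (gamma, shape 0.5). The rise is flatter but remains.

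**Per monitored day.** Under the same model, events per 100 monitored days are 0.1 (λ = 0.001) or 0.5 (λ = 0.005), at baseline and for every k. The dependence on cycles disappears.

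**Participants already in continuous AF.** If q of N dosed participants cannot have new AF, the percentage is multiplied by (N − q)/N. With assumed N = 20, q = 2 and 2 events, 2/20 = 10.0% (90% exact CI 1.8 to 28.3) is reported where the at-risk figure is 2/18 = 11.1% (2.0 to 31.0). For q = 1 and q = 3 the at-risk figures are 2/19 = 10.5% and 2/17 = 11.8%.

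**The case against.** The best defence is that the endpoint is not stated to be patch-based. Section 9.4.3 gives the device an exploratory purpose. AE reports, 12-lead ECGs at clinic visits and ICD downloads can all reveal arrhythmia, and they continue into stable dosing and washout. Medical history may also settle who had AF before. This stands as a limit on size: the figures above apply only to events the patch finds, and the effect is weaker in ICD carriers. It does not remove the problem. For participants without an ICD the patch is the only continuous monitor, and the number of ECG visits also grows with cycles.

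The study is a descriptive pilot with participant listings and no hypothesis test, and Section 10.4 defers technical detail to a SAP finalised before database lock. That is fair, and the SAP could deal with this. But the summary that is stated, a percentage of all dosed participants, is not comparable with screening or between people with different cycle counts.

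Four stronger readings are tempting but unsupported:
- A reader might infer that anyone in permanent AF would automatically count as an event. Continuous AF present at screening is not new and not clearly recurrent, so dilution is the likelier effect. Enrolment of such participants is also not certain.
- A reader might infer that the whole ICD row should be limited to carriers. That row includes resuscitated cardiac arrest, for which everyone is at risk.
- A reader might infer that the plan will produce a false dose-related signal. No arrhythmia table by dose or cycle count is described.
- A reader might extend 'new from screening' to the ventricular row. The qualifier belongs to AF/flutter only.

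**Conclusion.** The concern holds for patch-detected events. On-drug patch time ranges from about 14 to 140 days, and the planned crude incidence takes no account of it. With no drug effect, the share of AF labelled new would go from about 1% to 13%, or from about 6% to 47%, between 1 and 10 cycles at the two assumed rates. The direction follows from the schedule; the size depends on the assumed rates, on the patch being the source of detection, and on how many cycles people actually need. The upper limit of 10 cycles is derived from the 45-week figure, and visit windows or the redacted titration steps could shift it slightly.

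Distortion of the subgroup summaries is possible but not shown, since the documents do not say that cycle counts will differ between subgroups. The denominator for new AF/flutter is a smaller matter, about one percentage point in the example. These are primary safety endpoints and the remedy is cheap, so the change should be made.

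**What to change.** Keep the crude counts on the Safety Population and add the following to the SAP and table shells:

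1. State which sources feed each arrhythmia row, and define 'new' and 'recurrent'.
2. Report device-detected AF/flutter and ventricular events, and participants with an event, per analysable monitored day. For participants with an event, count wear time only up to the first one; otherwise the figure falls with longer wear.
3. Compare each on-drug recording with the screening recording within participant, as rates.
4. Show separately the events found clinically, by ECG, by ICD or as AEs.
5. Calculate new AF/flutter among participants not in persistent or permanent AF at baseline.
6. Give the ICD-therapy component an ICD-carrier denominator, and keep resuscitated cardiac arrest on the full Safety Population.
7. Footnote that stable dosing and washout have no scheduled device coverage.

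No new visit or procedure is needed. The costs are extra table rows whose denominators differ, and the work of deriving analysable wear time from the recordings uploaded to the central ECG vendor.

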Participants will receive once daily oral doses of MYK-224 and dose continuously throughout the treatment period. In Part A, all participants will begin with a dose of 5-mg MYK-224, which will then be increased or decreased based on [REDACTED]. The potential doses of MYK-224 may range from 2.5 mg to 50 mg, with the goal of identifying an effective target dose for each participant guided by echocardiographic response parameters. Dose titrations will occur every 4 weeks and be based on the TTE data collected the week before. Once the target dose is identified or the participant has titrated up to the maximum allowable dose, participants will continue at that dose until they a) have completed a minimum of 6 weeks total dosing at their target dose/the maximum allowable dose; and b) have completed a minimum of 12 weeks of treatment with MYK-224 at any dose. The duration of study participation in Part A will depend on the number of titrations needed to identify each participant's target dose or reach the maximum allowable dose and could range from [REDACTED] including Screening and the mandatory [REDACTED] washout for all participants prior to the end of study. The same titration process will be followed for both Cohort 1 and Cohort 2, unless data from Cohort 1 support an alternative dosing regimen.

For Part B (optional OLE), participation will be up to [REDACTED] including any necessary screening time and the mandatory [REDACTED] washout period following [REDACTED] of treatment with MYK-224.

For all participants, down-titration to the last tolerated dose or discontinuation of dosing for safety may occur at any time during treatment (Part A and Part B) based on the clinical judgment of the investigator in consultation with the Sponsor Medical Monitor.

Study Intervention:

Study Intervention for CV029009		
Medication	Potency	IMP/Non-IMP/AxMP
MYK-224	[REDACTED] mg	IMP

Abbreviations: AxMP, Auxiliary Medicinal Product; IMP, Investigational Medicinal Product.

Statistical Methods:

Primary analysis is to characterize the safety of MYK-224 in participants with oHCM. All the primary endpoints will be summarized descriptively. Descriptive summary statistics for continuous variables will include the number of participants, mean, standard deviation, median, minimum, and maximum. Categorical variables will be summarized using counts and percentages. Ninety percent exact confidence intervals will be presented, as appropriate.

Data Monitoring Committee: No

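### Primary safety incidences are planned as crude percentages by background-therapy subgroup, with no readable summary by dose or person-time, although Part A treatment runs from about 12 to 45 weeks

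*Combined protocol and SAP*

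**What the plan says.** Section 10.4.2 sets out three ways of summarizing the primary safety endpoints:

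- Adverse events and SAEs go by system "organ class, preferred term, and subgroup".
- For clinical events: "The incidence of cardiovascular events, hospitalizations, and arrhythmia will be listed by participants and summarized by subgroup".
- Laboratory tests, vital signs, ECG, TTE parameters, weight and examination findings "will be listed by participants and summarized by planned time point and subgroup".

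The two low-LVEF incidences in Table 10.4.2-1 have no sentence of their own. Whether they count as cardiovascular events or as TTE parameters, neither route brings in dose or time on drug. Section 10.4.1 fixes the statistic: "Categorical variables will be summarized using counts and percentages". Sections 5.2 and 10.2 show that subgroup means background therapy (monotherapy, beta-blocker, calcium channel-blocker, disopyramide combination).

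Exposure varies by design. Section 5.1 gives a "Treatment Period (variable between approximately 12 and 45 weeks" range. The schema note in Section 5.1.1 says: "Repeat 4-week titration period until target dose is identified or maximum allowable dose is reached". The protocol summary adds: "The potential doses of MYK-224 may range from 2.5 mg to 50 mg". It also says that the results are expected to help with dose selection in later studies.

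**The concern.** These are the primary endpoints of a single-arm study. No control group with the same spread of follow-up is available to absorb differences in duration. A percentage that pools a participant treated for 12 weeks with one treated for 45 depends on how long titration took as well as on the drug. The participants treated longest are, for the most part, those whose dose was raised furthest, so dose and duration move together and a pooled percentage cannot separate them.

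The only split that is planned may be affected too. Section 5.4 describes verapamil and diltiazem as moderate CYP3A4 inhibitors and allows Cohort 2 a different regimen. If titration length differs between background-therapy subgroups, their crude incidences compare unequal time on drug and unequal monitoring.

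The by-time-point tables raise a separate issue. Under Table 2-2 only participants whose dose is adjusted repeat the cycle, and under Section 7.4.1.1 those with a dose reduction move to stable dosing. A later-cycle summary therefore covers a selected remainder. The readable text does not say whether Titration Week 1 and Week 3 are pooled over cycles, which would mix doses, or kept apart, which would give shrinking and selected denominators.

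**Working it through.** **1. Treatment duration.** Inputs: a 4-week cycle (protocol summary); at least 6 weeks on the target dose, counting the 4 titration weeks (Section 5.1.1.2); and participants must "have completed a minimum of 12 weeks of treatment with MYK-224 at any dose". With *k* titration cycles:

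weeks = max(12, 4(*k* − 1) + 6)

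| *k* | 1 | 2 | 3 | 6 | 10 | 11 |
|---|---|---|---|---|---|---|
| weeks | 12 | 12 | 14 | 26 | 42 | 46 |

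This reproduces the stated minimum of 12. The stated 45 lies between 10 and 11 cycles. The titration steps are blacked out, so it can be neither confirmed nor contradicted.

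- Ratio of treatment times: 45/12 = 3.75.
- With 30 days (30/7 = 4.29 weeks) of adverse-event follow-up added to each: 49.29/16.29 = 3.03.
- Ratio of doses: 50/2.5 = 20.

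**2. Effect on a crude incidence.** Assume a constant event rate *r* per person-year, the same at every dose. The documents give no rate, so a range is shown. Incidence = 1 − exp(−*r* × weeks/52).

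| assumed *r* | 12 weeks | 45 weeks |
|---|---|---|
| 0.10 | 2.3% | 8.3% |
| 0.25 | 5.6% | 19.5% |
| 0.5 | 10.9% | 35.1% |
| 1.0 | 20.6% | 57.9% |

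The underlying rate is identical along each row; only the time differs.

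**3. Effect on detection.** Table 2-2 schedules TTE at Weeks 1 and 3 of each cycle, so titration alone gives 2*k* echocardiograms: 2 for one cycle, 20 for ten. Stable dosing adds others at an interval that is blacked out. Section 9.4.3 places the on-treatment rhythm monitor in two-week intervals within titration only. The visit names are blacked out; reading this as one interval per cycle gives 2*k* monitored weeks on treatment:

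- one cycle: 2 of 12 weeks (17%);
- ten cycles: 20 of 42 weeks (48%).

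Monitored time then grows 10-fold while treatment time grows 42/12 = 3.5-fold. Dividing by treatment time alone would not level the detection of monitor-found arrhythmia.

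**4. Who is left in later cycles.** Assume a constant chance *p* of leaving titration at each cycle (not in the documents). Share still titrating at cycle *k* = (1 − *p*)^(*k* − 1).

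| assumed *p* | cycle 5 | cycle 10 |
|---|---|---|
| 0.2 | 41% | 13% |
| 0.3 | 24% | 4% |
| 0.5 | 6% | 0.2% |

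**The case against.** The strongest reply is that this is an open-label pilot with no hypothesis test (Section 10.1), that every event is listed by participant, and that further tables belong in the SAP. Section 10.4 promises more detail there, and the exploratory and interim sections are not readable. This stands in part: absence from the readable text does not prove absence from the plan. But Section 10.4 says the SAP will elaborate the analyses described in that section, and none described there uses dose or person-time for events.

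Several stronger readings are tempting and are not supported:

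- *A reader might infer that nothing is analysed by exposure.* Section 10.4.3 plans graphical and regression analysis of concentration against LVEF, other TTE measures and all three gradients. It does not reach adverse events, heart failure events, arrhythmia, laboratory tests, vital signs or ECG.
- *A reader might infer that late cycles hold only non-responders.* They hold participants not at target before that cycle; some reach it at that cycle's Week 3 echocardiogram.
- *A reader might expect the tables to show fading efficacy.* Later cycles combine higher doses with less responsive participants, which pull in opposite directions, and the target rule is blacked out. No direction follows. The EOT-A gradient endpoints escape this selection.
- *A reader might expect incidence to climb across a planned table.* No planned event table has an axis for titration length. The problem is pooling.

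The 12-versus-45-week contrast also compares the two extremes. The actual spread of durations is unknown.

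**Conclusion.** The point holds for events. In the readable plan, adverse events, low-LVEF events, heart failure events, arrhythmia and other clinical events are reported as crude counts and percentages by background therapy. Treatment time behind them can differ 3.75-fold, dose 20-fold, and echocardiographic and rhythm surveillance also differ. At an assumed constant rate of 0.10 to 0.5 per person-year, incidence at 45 weeks is more than three times that at 12 weeks (8.3% versus 2.3%; 35.1% versus 10.9%) with no difference in risk per week. The pooled figures cannot show at which dose events occur.

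For TTE the point is narrower: time-point summaries at later cycles are selected and their definition is open, but the concentration-response analysis and EOT-A gradients already cover part of the need.

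The rates and the chance of leaving titration are assumptions. The durations, dose range and echocardiogram schedule come from the protocol. Because nothing is tested, what suffers is interpretation, not error rates. This is a worthwhile, inexpensive improvement and does not threaten the study's validity.

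**What to change.** 1. Beside the crude incidences, summarize adverse events, low-LVEF events, heart failure events and arrhythmia by dose at onset, with participant-weeks at that dose and rates per 100 participant-weeks. Give events after the last dose their own row. For low LVEF show the number of echocardiograms, and for monitor-detected arrhythmia the monitored weeks.
2. For TTE, laboratory tests, vital signs and ECG, state whether repeated titration cycles are pooled or kept separate. Add an anchored summary at Week 3 on the final titrated dose, with EOT-A as the other common visit.
3. If TTE is also shown by dose or by weeks since first dose, label it descriptive. Note that response-guided titration, and completion from about Week 12, select who contributes. The same caution applies to event rates at the higher doses.

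The cost is extra table shells in the SAP, which is still to be finalized before database lock. Section 7.6 already requires start, stop and dose-reduction dates, and Section 7.3 routes all dose adjustments through the IRT. Event onset dates are assumed to be on the case report form. Some dose cells will be sparse and should be presented descriptively. No dosing or clinical rule changes.
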